10.3.1.6 Clinical Global Impression of Improvement

The Clinical Global Impression of Improvement (APPENDIX I) is a clinician-rated instrument that measures the clinician's evaluation of change in subjects' overall improvement with treatment

AD-MW-07.08 18-Jun-2019 Page 48 of 101

on a scale where 1 and 7 using the same scale as for the PGI-C (see Section 10.3.1.5).

In this study, the CGI-I will be completed by the trained observer of the public speaking challenge, comparing the subject's anxiety level during the second public speaking challenge to the first public speaking challenge.

10.3.1.7

10.3.2 Safety Variables

Safety assessments will include the evaluation of AEs, clinical laboratory assessments, vital signs, 12-lead ECGs, physical examinations, HAM-D assessments, and C-SSRS evaluations.

10.3.2.1 Clinical Laboratory Safety Assessments

10.3.2.1.1 Clinical Laboratory Tests to be Performed

Samples for laboratory tests will be collected at the time points specified in the schedule of events (Table 2-1).

The following laboratory tests will be performed on site during the study:

- Urine pregnancy test (for all female subjects of child-bearing potential)
- Urine drug screen

The following laboratory tests will be performed by the central laboratory during the study:

Chemistry Panel: alanine aminotransferase, aspartate aminotransferase, albumin, calcium,

> chloride, alkaline phosphatase, bicarbonate, cholesterol, creatine kinase, creatinine, direct bilirubin, lactate dehydrogenase, magnesium, globulin, glucose, gamma-glutamyl transferase, indirect bilirubin, phosphorous, potassium, sodium, total bilirubin, total protein, triglycerides, urea

nitrogen, uric acid

hematocrit, hemoglobin, mean corpuscular hemoglobin, mean Hematology Panel:

corpuscular concentration, mean corpuscular volume, platelets, red blood

cell count, white blood cell count, red blood cell morphology

Hematology basophils, eosinophils, lymphocytes, monocytes, neutrophils

Differential Panel:

Urinalysis bilirubin, blood, clarity, color, glucose, ketones, leucocyte esterase,

Macroscopic Panel: nitrite, pH, protein, specific gravity, urobilinogen

12-Aug-2022 Amendment 3, Version 4.0 Page 49 of 101 Protocol PH94B-CL032

Urine Drug Screen: If on-site urine drug screen is positive, urine sample will be submitted to

central laboratory for confirmatory urine drug screens to be performed:

antidepressants, opiates, cocaine, benzodiazepines, amphetamines, barbiturates, cannabinoids, methadone, phencyclidine, propoxyphene,

methamphetamine, buprenorphine, ecstasy, oxycodone

Other: thyroid stimulating hormone

free thyroxine (T4) (if thyroid stimulating hormone is above the upper or below the lower normal limits, then free thyroxine will automatically be

performed)

The central laboratory should be used for any unscheduled and follow-up labs, if needed. Additional urine and blood samples may be collected for further evaluation of safety as warranted by the Investigator's judgment.

Results and reports from the central laboratory should be filed with the source documents for each subject. The central laboratory will provide laboratory results to the study site as soon as they are available; results will also be provided to Sponsor or designated data manager with agreed timelines.

Any laboratory value outside the normal range will be flagged for the attention of the Investigator, who must indicate whether or not the value is of clinical significance. If the result of any laboratory test performed during Screening is clinically significant, the subject should not be advanced to Visit 2. However, any abnormal result may be repeated to confirm the finding before excluding the subject from potential inclusion in the study. In addition, subjects should be excluded if they have any other abnormal laboratory test at Screening that, in the Investigator's judgment, is medically significant in that it would impact the safety of the subject, the conduct of the study, or the interpretation of the study results.

Follow-up/unscheduled laboratory tests may be performed on clinically significant abnormalities as indicated by the Investigator. Unscheduled laboratory tests may be repeated at any time at the discretion of the Investigator for appropriate medical care.

10.3.2.1.2 Specimen Handling Requirements

The transmission of infectious agents may occur through contact with contaminated needles and blood or blood products. Consequently, appropriate blood and body fluid precautions should be employed by all study personnel involved in the collection of blood and handling of specimens in both the clinic and laboratory settings. Refer to current recommendations of the appropriate authorities.

In addition to appropriate handling of subject samples, specific regulations exist regarding the shipment of biologic/etiologic samples. Procedures and regulations for the packaging and shipping of infectious samples are outlined in the study procedures manual or other appropriate reference.

AD-MW-07.08 18-Jun-2019 Page 50 of 101

The Investigator is responsible for ensuring that all study samples that are to be transported to another location are packed and shipped appropriately according to the applicable regulations.

10.3.2.1.3 Evaluation of Clinical Laboratory Values

The normal ranges of values for the clinical laboratory assessments in this study will be provided by the responsible laboratory and submitted to VistaGen Therapeutics, Inc. prior to the beginning of the study. They will be regarded as the reference ranges on which decisions will be made.

If a laboratory value is out of the reference range, it is not necessarily clinically relevant. The investigator must evaluate the out-of-range values and record his or her assessment of the clinical relevance in the appropriate eCRF.

All clinical laboratory values that in the investigator's opinion show clinically relevant or pathological changes during or after termination of treatment must be reported as AEs and followed, as described in Section 11.2.5.

All measurements described in this section are recognized standard methods.

10.3.2.2 Clinical Examinations

10.3.2.2.1 Vital Signs

Vital signs, including heart rate, respiratory rate, and seated systolic and diastolic blood pressure will be measured after the subject has been in a seated position for 5 minutes. Temperature will also be measured.

10.3.2.2.2 Twelve-lead Electrocardiogram

A standard 12-lead ECG will be performed after the subject has been seated for at least 5 minutes. All ECG recordings will be identified with the subject number, initials, date, and time of the recording and will be attached to the subject's eCRF.

10.3.2.2.3 Physical Examination

A complete physical examination (excluding the genitourinary examination) will be performed as indicated in the schedule of events (Table 2-1). The physical examination will include measurement of weight and height, and an examination of the nasal passages.

10.3.2.2.4 Hamilton Depression Scale

The Hamilton Depression scale is a 17-item instrument that evaluates symptoms of expression experienced over the past week (see APPENDIX G). Items are scored on a variety of scales, including 3-, 4-, and 5-point questions. An overall score of 0 to 7 is generally accepted to be within the normal range, while a score of 20 or higher indicates at least moderate severity.

10.3.2.2.5 Columbia-Suicide Severity Rating Scale

The C-SSRS is a semi structured interview that captures the occurrence, severity, and frequency of suicide-related thoughts and behaviors during the assessment period. The interview includes

Page 51 of 101

12-Aug-2022

definitions and suggested questions to solicit the type of information needed to determine if a suicide-related thought or behavior has occurred. The C-SSRS has a "baseline" version which will be completed at Screening and a "since last visit" version that will be completed at all subsequent visits. There are a maximum of 19 items to be completed: 7 that are required, 10 potential additional items if there is a positive response to a required item, and 2 items for suicide/suicide behavior present during the interview. The C-SSRS uses dichotomous scales (i.e., yes or no), Likert scales, and text or narrative to further describe the thoughts or behaviors.

10.3.2.3 Adverse Events

The definitions and management of AEs, and any special considerations for AEs, are provided in Section 11.

Amendment 3, Version 4.0 12-Aug-2022 Page 52 of 101

11. ADVERSE EVENTS

It is the responsibility of the Investigator at the site to oversee the safety of the study at his/her site. This safety monitoring will include careful assessment and appropriate reporting of SAEs as noted in this section. Medical monitoring will include a regular assessment of the number and type of SAEs.

11.1. Definitions

11.1.1 Adverse Events

An AE is defined as any untoward medical occurrence in a patient or clinical investigation subject administered a pharmaceutical product that does not necessarily have a causal relationship with this treatment. An AE can therefore be any unfavorable and unintended sign (including an abnormal laboratory finding, for example), symptom, or disease temporally associated with the use of a medicinal product, whether or not related to the medicinal product.

Pre-existing diseases or conditions will not be considered AEs unless there is an increase in the frequency or severity, or a change in the quality, of the disease or condition. (Worsening of a pre-existing condition is considered an AE.)

In this study, AEs will be classified by time of occurrence and Visit 3 group assignment to more clearly identify those arising after exposure to placebo only and those arising after exposure to PH94B.

Pregnancy is not considered an AE, but it is an important medical event, which must be followed up as described in Section 11.3.1.

11.1.2 Unexpected Adverse Event

An expected AE is one for which the nature or severity is consistent with the known AE profile of the product. For a pre-approval test product, the known information is contained in the IB. For a marketed product, the known information is contained in the current package insert for the product.

An unexpected adverse event (UAE) is one for which the nature or severity of which is not consistent with the applicable product information (e.g., IB for an unapproved investigational product or package insert/summary of product characteristics for an approved product). For example, hepatic necrosis would be unexpected (greater severity) if the IB only listed elevated hepatic enzymes or hepatitis. Likewise, cerebral thromboembolism and cerebral vasculitis would be unexpected (greater specificity) if the IB only listed cerebral vascular accidents.

Furthermore, reports that add significant information on specificity or severity of a known, already documented adverse reaction constitute unexpected events. Examples would be (a) acute renal failure as an expected adverse reaction with a subsequent new occurrence of interstitial nephritis (interstitial nephritis would be unexpected) and (b) hepatitis with a first occurrence of fulminant hepatitis (fulminant hepatitis would be unexpected.)

11.1.3 Serious Adverse Events

An SAE is any untoward medical occurrence that at any dose:

• results in death

Page 53 of 101

12-Aug-2022

• is life-threatening

NOTE: The term "life-threatening" in the definition of "serious" refers to an event in which the subject was at risk of death at the time of the event; it does not refer to an event that hypothetically might have caused death if it were more severe.

- requires inpatient hospitalization or prolongation of existing hospitalization An elective hospital admission to treat a condition present before exposure to the IP, or a hospital admission for a diagnostic evaluation of an AE, does not qualify the condition or event as an SAE.
- results in persistent or significant disability/incapacity
- is a congenital anomaly

NOTE: A congenital anomaly in an infant born to a mother who was exposed to the IP during pregnancy is an SAE. However, a newly diagnosed pregnancy in a subject that has received an IP is not considered an SAE unless it is suspected that the IP(s) interacted with a contraceptive method and led to the pregnancy.

• is an important medical event

NOTE: Medical and scientific judgment should be exercised in deciding whether it is appropriate to consider other situations serious, such as important medical events that may not be immediately life-threatening or result in death or hospitalization but may jeopardize the subject or may require intervention to prevent one of the other outcomes listed in the definition above. Examples of such events are intensive treatment in an emergency room or at home for allergic bronchospasm, blood dyscrasias, or convulsions that do not result in hospitalization, development of drug dependency, or drug abuse.

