11.3. Special Considerations

11.3.1 Pregnancy

All women of childbearing potential who participate in the study should be counseled on the need to practice adequate birth control and on the importance of avoiding pregnancy during study participation. Women should be instructed to contact the investigator or study staff immediately if pregnancy occurs or is suspected.

Pregnancy testing will be conducted prior to administration of the IP on every woman of childbearing potential. A woman who is found to be pregnant at the Screening Visit will be excluded from the study and considered to be a screening failure.

A woman who becomes pregnant during IP treatment or within 7 days of discontinuing the IP will be immediately discontinued from study participation. The investigator must report the pregnancy within 48 hours of learning of the pregnancy, to Premier Research Pharmacovigilance using the Pregnancy Data Collection Form via the same fax number and/or email address as for SAE reporting. The investigator should contact the designated individual(s) who receive SAE notification and record information related to the pregnancy on an Exposure in Utero form provided by the sponsor or its designee.

Early Termination Visit assessments are required as soon as possible after learning of the pregnancy. The investigator is also responsible for following the pregnancy until delivery or termination. These findings must be reported on the Exposure in Utero form and forwarded to the designated individual(s). The event meets the SAE criterion only if it results in a spontaneous abortion or a congenital anomaly.

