12. DATA SAFETY MONITORING BOARD

A data safety monitoring board will not be used in this study.

12-Aug-2022 Amendment 3, Version 4.0
AD-MW-07.08 18-Jun-2019 Page 60 of 101

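### An AE whose only seriousness ground is a diagnostic admission is classed non-serious (Protocol 11.1.3), and Protocol 11.1.1, 11.1.3 and 11.3.1 disagree on when a pregnancy is an SAE

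*Protocol*

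**What the plan says.** **Hospital admission.** Under Protocol 11.1.3 an AE is serious if it "requires inpatient hospitalization or prolongation of existing hospitalization". The same bullet then sets two exclusions. One is an elective admission to treat a condition that existed before exposure to the investigational product. The other reads "a hospital admission for a diagnostic evaluation of an AE, does not qualify the condition or event as an SAE". A later criterion, the important medical event, is left to discretion: "Medical and scientific judgment should be exercised in deciding whether it is appropriate to consider other situations serious".

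**Pregnancy.** Three places speak to its status:
- Section 11.1.1: "Pregnancy is not considered an AE, but it is an important medical event".
- Section 11.1.3, in the note on congenital anomaly: a newly diagnosed pregnancy "is not considered an SAE unless it is suspected that the IP(s) interacted with a contraceptive method and led to the pregnancy".
- Section 11.3.1: "The event meets the SAE criterion only if it results in a spontaneous abortion or a congenital anomaly".

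**What depends on the classification.** The investigator judges seriousness against 11.1.3 (Section 11.2.2.2). SAEs go to the contract research organisation within 24 hours (11.2.6.1). Non-serious AEs go on the eCRF and reach the sponsor under a safety management plan, for which 11.2.6.2 states no clock. For pregnancy, "The investigator must report the pregnancy within 48 hours of learning of the pregnancy" (11.3.1). The opening of Section 11 describes medical monitoring as a regular review of SAEs. SAP 9.1.2 tabulates serious TEAEs and lists SAEs. Section 12 states: "A data safety monitoring board will not be used in this study".

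**The concern.** An unexplained event after dosing that leads to an unplanned admission for work-up is a case in which early notice to the sponsor is useful. As written, the reason for admission alone is enough to remove the hospitalisation ground, and the protocol gives no rationale for going beyond elective admissions. On pregnancy, a site with a suspected contraceptive interaction finds one section that allows SAE status and another that denies it.

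At stake is the completeness and timeliness of this trial's serious-event reporting. There is no safety board, and the interim analysis in Protocol 13.1.6 is described in terms of SUDS data and conditional power. SAE reporting is therefore the main expedited safety route that the documents describe. Subjects may also move on to up to 12 months of open-label PH94B (Protocol 10.1), so early recognition of an unexplained event has value beyond this trial.

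**Working it through.** The plan states no figure on this point, and no rate of diagnostic admissions or pregnancies is given. The check is a comparison of the sections.

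**1. How far the diagnostic-admission exclusion reaches**

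| Admission | Limited to conditions present before exposure? | Effect under 11.1.3 |
|---|---|---|
| Elective, for treatment | Yes | Hospitalisation ground removed |
| To evaluate an AE diagnostically | No | Hospitalisation ground removed |
| To treat a new AE | Not excluded | Serious |

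Two cases follow from the second row.
- *The AE also meets another criterion* (death, threat to life, disability, congenital anomaly, important medical event). The exclusion removes only the hospitalisation ground, so the AE remains an SAE.
- *The diagnostic admission is the only ground.* The AE is non-serious. The 24-hour rule in 11.2.6.1 does not apply, the SAE review in Section 11 does not count it, and it does not enter the serious-TEAE tables or SAE listing of SAP 9.1.2.

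The important-medical-event clause is a partial backstop for the second case. It rests on judgment, and its examples are events managed without admission, such as intensive emergency-room treatment. An emergency-room case is thus offered as an example of a serious event, while an inpatient work-up is expressly said not to qualify. An investigator could reasonably stop at the exclusion.

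**2. The pregnancy rules, case by case**

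| Case | 11.1.3 note | 11.3.1 |
|---|---|---|
| Interaction suspected; no spontaneous abortion or anomaly | SAE status allowed | Not an SAE |
| Congenital anomaly | SAE | SAE |
| Spontaneous abortion; no interaction suspected | Note addresses the new pregnancy, not this outcome | SAE |
| None of these | Not an SAE | Not an SAE |

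The first row is a direct contradiction: the clock is 24 hours if the case is an SAE and 48 hours if it is only a pregnancy report. In the last row the two sections agree, but 11.1.1 labels every pregnancy with the words that 11.1.3 uses for an SAE criterion, so even that case is not clean.

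**3. What is still captured**

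Protocol 11.2 requires every AE, serious or not, to be recorded on the eCRF. SAP 9.1 summarises TEAEs by system organ class, preferred term, severity and relationship. An AE affected by the exclusion stays in those data if it is treatment-emergent; it loses the serious label and the 24-hour clock.

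**The case against.** The strongest reply is that the exclusion sits inside the hospitalisation bullet and qualifies it. A reader might infer that the protocol breaks its own hospitalisation criterion. It does not: an excluded event meets the opening words of the bullet but not the bullet as qualified. This half of the point is an over-broad definition; only the pregnancy half is a contradiction. That objection stands.

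Several other stronger readings are also unsupported:
- *Undiagnosed events are lost.* They remain on the eCRF and in the TEAE summaries. AEs are also followed until they resolve, stabilise or are explained (Protocol 11.2.5), so the result of a work-up can still make an event serious.
- *The statements that no SAEs have occurred rest on this definition.* Those in the Synopsis and in Protocol 5.2.2 and 7.3 describe earlier experience with PH94B, and the SAE definitions used there are not given.
- *SAE reporting is the only expedited check.* Pregnancy has its own 48-hour route to the same pharmacovigilance contact, and the timelines in the safety management plan are not shown.
- *Binomial bounds for no event or one event among 104 subjects show the size of the problem.* They would suit any safety remark about an arm of that size and do not measure what this clause does.

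It is also fair to say that the pregnancy conflict will seldom arise: randomised exposure is a single dose, follow-up is about one week, and either report goes to the same recipient. That limits its frequency, but a site facing the case still cannot follow both sections.

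**Conclusion.** The point holds in two separate parts. First, the diagnostic-admission exclusion is wider than its neighbour and moves an AE with no other seriousness ground out of 24-hour reporting, SAE-based medical monitoring and the serious-TEAE tables, unless the investigator chooses the important-medical-event route. Second, Protocol 11.1.3 and 11.3.1 give incompatible conditions for a pregnancy to be an SAE, with a 24-hour or 48-hour consequence, and the wording of 11.1.1 adds to the confusion. The pregnancy conflict does not follow from the hospitalisation rule and should be handled as its own item.

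The number of affected events cannot be estimated from the documents and is expected to be small. No primary or secondary efficacy result is touched. The first part assumes that investigators apply 11.1.3 as written and that the safety management plan, which is not shown, does not already impose a 24-hour clock on such admissions; if it does, the effect shrinks to the serious label and the tables. With no safety board and an inexpensive remedy, the correction is worth making.

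**What to change.** Two changes to the protocol:
1. In 11.1.3, remove the diagnostic-admission phrase, so that the only admission excluded is the elective one for a condition present before exposure.
2. Reconcile 11.1.1, 11.1.3 and 11.3.1 into one statement of when a pregnancy is reported as an SAE and on which clock, and have the other sections refer to it. Replace the label in 11.1.1 if pregnancy is not meant to fall under the important-medical-event criterion.

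Protocol 14.8 allows changes only through a formal amendment with investigator signature and IRB approval, so a memo to sites would not be enough. The text is a few sentences, and the SAP tables need no redesign because they use the investigator's classification. The downside is possibly a few more SAE reports.

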11.1.4 Significant Adverse Events

Other significant AEs are defined as marked hematological and other laboratory abnormalities (other than those meeting the definition of serious) and any events that led to an intervention, including withdrawal of test drug, dose reduction, or significant additional concomitant therapy.

